#### 6.5 Clinical Laboratory Parameters

Only scheduled laboratory parameters, as specified in Error! Reference source not found.2, will be included in the laboratory results summaries, unless specified otherwise. All laboratory data, including those collected at unscheduled visits/time, will be included in the listings.

Quantitative results (actual values and change from baseline) will be summarized for each scheduled time by treatment group and overall. For each parameter, the mean ( $\pm$  SE) at each scheduled time will be plotted for its actual value and its change from baseline. Data collected at the End-of-study/treatment (EOS/ET) time will be included as one time point regardless of subjects' EOS status.

In addition, when deemed necessary, shift tables based on lab normal ranges (e.g., below/within/above the normal range), where the shift is from baseline to last clinic visit will be provided.

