11.6. Safety Analysis

All the safety endpoints will be analyzed in the SA Population. Additional safety analyses will be conducted on the mITT and PP Population if they are different from the SA population.

The incidence of all AEs occurring after the start of the CPB procedure will be summarized by treatment group using frequency and percentage. AEs that occur following informed consent but prior to the start of CPB will not be included in this safety analysis but will be provided in a listing. Within the Safety Analysis, AEs will be summarized by severity and relationship to the study device as determined by the Investigator (or designee). Discontinuations due to AEs, and SAEs will be summarized. All AEs will be coded using the Medical Dictionary for Regulatory Activities (MedDRA®) according to system organ class and preferred term, prior to database lock.

Observed values for clinical laboratory test data and vital signs, along with change from baseline results, will be summarized by collection time point. A summary of clinically notable values will be provided.

All the safety data will be listed in the SA population. Further details regarding presentation and analysis of safety data will be detailed in the SAP.

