An unanticipated adverse device effect (UADE) is any adverse device effect which by its nature, incidence, severity or outcome has not been identified in the current version of the risk analysis report. These events can be classified as either serious or not serious in accordance with the definition for SAEs above. In the event of a possible UADE, the subject blind may be broken as per **Section 6.3.3** above. This will enable confirmation of relationship between the adverse event and device exposure and facilitate appropriate safety procedures as well as regulatory reporting per guidelines.

Anticipated Adverse Events/Device Related Adverse Events

A variety of complications are expected to occur in subjects undergoing CPB and cardiothoracic surgery, regardless of whether or not DrugSorb™-ATR is used. These may include, but are not limited to:

Serious, but less common, risks:

- Bleeding during or after the surgery including bleeding in relation to anticoagulation
- Blood clots that can cause heart attack, stroke, or lung problems
- Heparin-induced thrombocytopenia
- Bypass induced thrombocytopenia
- Reduction in platelets
- Infection, including pneumonia
- Organ injury including:
 - Respiratory damage causing breathing problems or failure to wean from the ventilator
 - Cardiac dysrhythmias/arrhythmias
 - Kidney injury or renal failure
 - Cognitive impairment
- Death

Less serious, but more common risks and adverse events:

- Low-blood pressure
- Nausea and/or vomiting
- Hypothermia and/or Chills
- Allergic response to device materials
- Reduction in platelet count
- Reduction in white blood cell count
- Reduction in proteins (albumin, total protein)
- Coagulation within device
- Heparin-induced thrombocytopenia

Potential Adverse Device Events Directly Related to DrugSorb™-ATR:

- Removal of drugs and hormones
- Allergic response to device materials
- Reduction in platelet count
- Reduction in white blood cell count
- Reduction in proteins (albumin, total protein) which may increase with CPB duration.
- Reductions in serum calcium (as a consequence of reductions in albumin)
- Coagulation within device
- Infection
- Blood loss
- Hemolysis
- Device leakage
- Circuit leakage
- Death

Investigator Reporting:

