- ⁿ All AEs will be recorded from point of authorization to participate in the study through the 30-day Follow-up. Serious AEs occurring after 30 days post-operation are to be reported to the Sponsor if, in the judgment of the Investigator, there is concern for potential association between the event and the use of the DrugSorb™-ATR device.
- ^o If subject is intubated/requires mechanical ventilatory support, the maximum ventilation and mechanical support requirements will be recorded for each day.
- ^p Documented in the ABG eCRF; only required if the subject is intubated or on mechanical ventilatory support
- ^q The maximum vasopressor dosage will be recorded each day.
- ^r Physical exam performed on the day of screening as part of standard of care but occurring prior to signing of informed consent *may* be used for the screening PE. The physical exam and medication history will be repeated on the day of the procedure, if the day of the procedure is different than the day of screening
- ^s Assessments completed daily ***through hospital discharge***.
- ^t In the advent of any cardiac ischemic AEs, EKG (to assess for Q waves) and cTn **must** be obtained. EKG will be provided as source documentation for CEC adjudication. cTn will be documented within the laboratory eCRF for CEC event adjudication
- ^u Through postoperative day 2 only.

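### The optional laboratory shift table in SAP 6.5 ends at an undefined last clinic visit and can understate how many subjects had an early fall in platelets, white cells, albumin, total protein or calcium

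*SAP*

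**What the plan says.** SAP 6.5 (Clinical Laboratory Parameters) has two layers.

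- **Main analysis.** "Quantitative results (actual values and change from baseline) will be summarized for each scheduled time by treatment group and overall". Means with standard errors "at each scheduled time will be plotted for its actual value and its change from baseline". "All laboratory data, including those collected at unscheduled visits/time, will be included in the listings".
- **Optional addition.** "In addition, when deemed necessary, shift tables based on lab normal ranges" are to be made, "where the shift is from baseline to last clinic visit will be provided".

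The schedule is in Protocol Appendix 4, Table 6. Hematology, clinical chemistry and the coagulation panel are required after surgery at ICU admission, POD1 and POD2. Footnote u on the POD2 entry reads "Through postoperative day 2 only". From POD3 the entries are standard of care, which Protocol Section 9 makes optional. The day-30 column has no laboratory entry, and Protocol 9.1 allows that contact to be a telephone call or a record review.

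Protocol Appendix 1 and SAP 6.2.2 list falls in platelets, white cells, proteins and serum calcium as potential direct effects of the device. One entry is "Reduction in proteins (albumin, total protein) which may increase with CPB duration". Protocol 5.1 limits device use to the bypass period.

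Protocol 11.6 adds a further commitment, "A summary of clinically notable values will be provided", and leaves details of the safety analysis to the SAP. SAP 6.5 contains neither that summary nor thresholds for it.

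**The concern.** The shift table is the only place in SAP 6.5 where subjects would be classified against a normal limit, and its end point suits a different question. If exposure stops when bypass stops, a direct effect on blood composition should be sought in the first postoperative samples. A comparison with the last available value describes where subjects ended up. A subject who was low at ICU admission and normal at the last draw appears as normal to normal.

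The end point is also loosely specified. If optional later draws count, the time of the last value depends on length of stay and local practice. Both could differ by arm: Protocol 5.2 names a shorter hospital stay as a potential benefit, and Protocol 11.1 assumes 0.32 platelet units in the treatment arm against 1.6 in control. The last-value category could therefore partly reflect discharge timing and transfusion, in either direction.

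At stake is the clarity of a safety display for effects the sponsor itself lists as device risks, in a trial that has establishing safety among its objectives.

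**Working it through.** The plan states no figure on this point, so there is none to reproduce. The check sets the passages side by side.

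**1. What can last clinic visit mean for laboratory data?**

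| Reading | Support | Difficulty |
|---|---|---|
| POD2 | Last required draw in Table 6 | SAP 6.5 does not say so |
| Last optional draw, POD3 to 29 | Table 6 lists these as standard of care | Present for some subjects only; time varies |
| End of study or early termination | SAP 6.5 treats this as one time point | Table 6 schedules no laboratory test at day 30 |

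The SAP does not choose between them.

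**2. Are the early values available?** Platelet count, white cell count, albumin, total protein and calcium are all in Protocol Appendix 2. None carries the footnote that restricts a test to routine care (ionized calcium and the white cell differential do). All five are therefore required at ICU admission, POD1 and POD2.

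**3. What would a last-value table retain?** Let p_T and p_C be the shares below normal at an early draw in the treatment and control arms, and r the share of those subjects back in range by the last value. If r is the same in both arms and no new subject falls below normal later, then

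last-value difference = (p_T − p_C) × (1 − r).

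The documents give none of these quantities. Over the whole range, the table keeps the full early difference at r = 0 and none of it at r = 1. If r differs between arms, the difference can move either way. The mechanism is clear, but its size is not known.

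**4. What would the main analysis show?** As a gauge only, assume 65 subjects per arm with values (the evaluable number in SAP Section 2; the safety population may differ) and a common SD. At one time point:

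- 95% confidence interval half-width for the difference in means = 1.96 × √(2/65) = 0.34 SD.
- Approximate power at two-sided 0.05 for a between-arm shift of d SDs = Φ(d/√(2/65) − 1.96): 40% for d = 0.3, 81% for d = 0.5 and 98% for d = 0.7.

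The SAP plans no formal test of these means. The figures indicate only that a moderate early mean shift would probably be visible without a shift table. A marked fall confined to a minority moves the mean less.

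**5. Which planned output counts subjects who crossed a normal limit early, by arm?** The summaries in SAP 5.1 and 6.5 give n, mean, SD, median, minimum and maximum. Listings are not a comparison between arms. Adverse-event tables count subjects, but only for changes the investigator judged clinically significant (Protocol 9.2.1). The shift table counts subjects at the last value. None gives the early count.

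**The case against.** The strongest case on the other side is that the shift table is an optional supplement, and that the main outputs already cover the times at which an effect is expected.

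- By-arm summaries include the minimum and median at ICU admission, POD1 and POD2.
- Protocol 9.2.1 requires clinically significant laboratory changes to be recorded as adverse events and gives the need for medical intervention as its example. A platelet fall treated by transfusion fits. SAP 6.3 then tabulates subjects by preferred term, severity and relation to the device.
- Postoperative platelet and red-cell transfusions are compared between arms in SAP 5.4.1.2.
- Recovery by the last value is not documented. If that value is POD2, it lies within the early period.
- Protocol Appendix 1 expects falls in platelets, white cells and proteins after bypass with or without the device, so a worst-value table may show many low subjects in both arms.
- Table shells are in a separate document (SAP Section 8) and may say more.

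Most of this stands. A reader might infer from the last-visit end point that device-related falls would be missed altogether; the documents do not support that, given the outputs above. Two things remain. No planned output in SAP 6.5 counts early crossings of a normal limit by arm, and the adverse-event route depends on investigator judgement without numeric thresholds. The undefined visit and the absent notable-values summary do not depend on any assumption about recovery.

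**Conclusion.** The point holds as a minor safety-reporting matter. The end point of the shift table is undefined for this trial's laboratory schedule. It also fits poorly with an exposure confined to bypass, and can understate the number of subjects with an early, transient or transfusion-corrected fall in the five analytes. Mean shifts and clinically significant falls would still be seen elsewhere.

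The understatement cannot be quantified from the documents: it runs from nothing to the whole early difference, depending on recovery. The conclusion assumes that direct effects appear early, which follows from the limited exposure but is not shown by any time course in the documents. That the notable-values summary is not carried into SAP 6.5 is a plain mismatch with Protocol 11.6, subject to what the separate table shells contain. The primary analysis, alpha and sample size are unaffected.

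**What to change.** Before unblinding, amend SAP 6.5 as follows.

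1. For platelets, white cells, albumin, total protein and calcium, make unconditional a normal-range shift from baseline to the lowest scheduled value from ICU admission through POD2, by arm, in the SA and i-CABG SA populations.
2. Keep a second column for a defined last value, for example POD2, to show recovery.
3. Carry forward the summary of clinically notable values from Protocol 11.6, with its thresholds stated in advance.

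The cost is SAP wording and one more table for the shift, plus the notable-values summary already promised. No new data are needed.

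Two limits apply. Many subjects in both arms may be low after bypass, so the table should be read beside the change from baseline at each time. The lowest scheduled value is also not the true nadir: when several sets are drawn on one postoperative day, Protocol 9.2.3 asks for the one nearest the nominal time, and an early transfusion can still mask a fall between draws.

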**Table 2: Clinical laboratory parameters**

Clinical chemistry	Hematology
--------------------	------------

 
Alanine aminotransferase
 
Albumin
 
Alkaline phosphatase
 
Aspartate aminotransferase
 
Blood urea nitrogen
 
Calcium
 
Chloride
 
Creatinine
 
Direct bilirubin
 
Glucose
 
Potassium
 
Sodium
 
Total bilirubin
 
Total protein
 
	Hematocrit Hemoglobin Platelet count Red blood cell count White blood cell (WBC) count
Coagulation tests:  Coagulation Panel: 
 
Activated partial thromboplastin time
 
International normalized ratio
 
Prothrombin time
 
Fibrinogen
 
 Point of Care Test(s): Activated clotting time (ACT) Arterial blood gas (ABG)	Other, including cardiac biomarkers 
 
Cardiac troponin (cTn)
 

## 6.6 Vital Signs

A descriptive summary of vital sign values, including changes from baseline, will be provided by scheduled time point by treatment group and overall.

The above summary will be provided for the following vital sign variables:

- Systolic blood pressure (mmHg)
- Diastolic blood pressure (mmHg)
- Body temperature (°F)
- Heart rate (beats per minute)
- Respiratory rate (breaths/minute)
- Oxygen saturation (SaO2) (%)

Vital signs data will be listed by subject for all subjects in the safety population.

## 6.7 12-Lead Electrocardiogram (ECG)

A descriptive summary of ECG values, including changes from baseline (where present), will be provided by time point by treatment group, for the following ECG variables:

- Heart rate (bpm)
- PR interval (msec)

- RR interval (msec)
- QRS duration (msec)
- QT interval (msec)
- QTcB interval (msec)
- QTcF interval (msec)

## 7 DEFINITIONS AND CONVENTIONS FOR HANDLING OF THE DATA

### 7.1 Handling of Partial Dates of Concomitant Medication

Partial start dates of prior and concomitant medication will be assumed to be the earliest possible date consistent with the partial date. Partial stop dates of prior and concomitant medications will be assumed to be the latest possible date consistent with the partial date. In the case of completely missing stop date, medication use will be assumed to be ongoing.

### 7.2 Reporting Precision

Summary statistics will be presented to the degree of precision in **Error! Reference source not found.**, unless otherwise

**Table 3: Degree of Precision**

Statistics	Degree of Precision
Mean, Median, Quartiles, Confidence limit boundaries	One more than the raw data, up to 3 decimal places.
Standard deviation, Standard error	One more than the mean, up to 3 decimal places
Minimum, Maximum	The same as the raw data, up to 2 decimal places
p-value	Rounded to 3 decimal places and therefore presented as 0.xxx; p-values smaller than 0.001 as '<0.001'; p-values greater than 0.999 as '>0.999'.
Percentage	One decimal place. A percentage of 100% will be reported as 100%. Percentages of zero will be reported as 0.

Fractional numeric values will be presented with a zero to the left of the decimal point (for example, 0.12 to 0.30).

For weight, height, and body mass index (BMI), one decimal place will be used for summary statistics.

## 8 MOCK TABLES, LISTINGS, AND GRAPHS (TLGS)

Mock-up tables and listings will be provided in a separate document.

## 9 PHARMACOKINETIC ANALYSIS

The statistical analysis plan for the pharmacokinetic analysis of plasma ticagrelor and TAM concentration are presented in **Appendix A**.

## APPENDIX A: STATISTICAL ANALYSIS PLAN FOR PHARMACOKINETIC ANALYSES

### A 1.0 Pharmacokinetic Analyses

The pharmacokinetic (PK) analysis set will include subjects with at least one sample collected and analyzed for plasma drug concentration. The PK analysis set will be the primary set for PK analyses. The PK analyses will be performed for the mITT, PP, i-CABG mITT, and i-CABG PP populations.

### A 1.1 Pharmacokinetic Assessment

#### A 1.1.1 Sample Collections for Pharmacokinetic Analysis

PK Blood samples will be collected for the determination of plasma ticagrelor and desethoxyhydroxy ticagrelor (ticagrelor active metabolite, TAM) concentration. The pre-CPB blood sample will be drawn prior to the start of CPB and can be up to 2hrs prior to skin incision. During the procedure, while the subject is on CPB, serial samples will be drawn at  $30\pm15$ min following initiation of CPB, at 60min, at 90min, and at 120min of CPB time. If the total CPB time required for the procedure is  $<120$ min (2hrs), the serial sampling will only be performed through the required duration of CPB. A post-CPB sample will be obtained as soon as possible following the end of CPB, and no later than 30min after the subject has been disconnected from the CPB circuit. The actual date and time of collection of each PK sample will be recorded.

#### A 1.1.2 Handling Missing or Below the Lower Limit of Quantification Data

For PK concentration data, if the actual sampling time is missing, but a valid concentration value has been measured, the concentration value will be flagged, and the scheduled time point may be used for the calculation of PK parameters. In cases of missing concentration data, the missing data will not be imputed. For the individual concentration and PK parameter calculation of each group, the following rules will be applied:

- If BLQ values occur between measurable concentrations in a profile, the BLQ should be omitted (set to missing, and the time point is ignored in computations).
- If a BLQ value occurs after the last measurable concentration in a profile, the BLQ should be treated as missing data.
- If two BLQ values occur in succession after the last measurable value, the profile is deemed to have terminated at the first BLQ value and any subsequent concentrations and time points are omitted from pharmacokinetic calculations.

For the concentration summary and mean concentration plot preparation of each group, the following rules will be applied:

2. Mean concentration at any individual time point will only be calculated if at least half of the subjects have valid values (i.e., quantifiable and not missing) at this time point for each arm.

- In cases where a mean value is not calculated due to the above criterion not being met, the value will be set to missing.
- BLQ values will be set to zero.

GM and GM CV% will not be calculated if there are zero values for concentrations.

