#### **5.3.1 Key Secondary Effectiveness Endpoints**

There is no imputation for the missing pre- or post-CPB blood ticagrelor levels, and analysis will be limited to subjects who have both samples.

Percent difference in pre-CPB vs. post-CPB blood ticagrelor levels as measured by LC/MS-MS is the key secondary effectiveness endpoint.

This endpoint will be evaluated using the two-sample t-test for the percentage change in blood ticagrelor levels between the treatment and the control group. The p-value and 95% CI for this treatment difference will be provided. The model assumption will be checked using the observed data.

If the post-CPB blood ticagrelor level is below the limit of quantification (BLQ), the BLQ value will be assigned.

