#### **5.3.2 Sensitivity Analysis**

Wilcoxon rank sum test based on the observed data will be performed as a sensitivity analysis. The nonparametric p-value will be provided as well as median treatment difference in percent change between pre-CPB and post-CPB blood ticagrelor levels.

The Last Measurable Observation Carried Forward method will be implemented to test the validity of imputation.

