#### A 1.1.4 Pharmacokinetic Parameters

The following plasma PK parameters of ticagrelor and TAM will be determined with actual sampling time points using noncompartmental methods as appropriate:

Parameters	Description
AUC 0-t	Area under the plasma concentration vs time curve (AUC) from pre-dose (time 0) to the last quantifiable plasma concentration (C last )

No PK parameters will be calculated for subjects with 2 or fewer detectable concentrations in their PK profile.

AUC and plasma concentration for ticagrelor and TAM at each sampling timepoint (Pre-CPB, 30min, 60min, 90min, 120min, and post-CPB) will be compared between control and DrugSorb using a two-sample t-test, and if parametric assumptions are not met, then via a Mann-Whitney test.

The sample SAS code for this analysis is included here

```
proc ttest data=ADPP sides=2 alpha=0.05 h0=0;
  class TREATMENT;
  var log_PKParm;
  ods output ConfLimits=CL Statistics=Stat Ttests=Ttest;
```

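### Two below-quantification (BLQ) rules around the key secondary need changing: the carry-forward check, and the missing rule for the time-point concentration comparison

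*SAP*

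**What the plan says.** **Key secondary, main analysis (SAP 5.3.1).** "If the post-CPB blood ticagrelor level is below the limit of quantification (BLQ), the BLQ value will be assigned". I read this as assigning the LLOQ. Missing pre- or post-CPB samples are not imputed.

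**Key secondary, sensitivity (SAP 5.3.2).** After a Wilcoxon test on the observed data: "The Last Measurable Observation Carried Forward method will be implemented to test the validity of imputation". The only imputation in 5.3.1 is the BLQ assignment, so that is what is being tested. SAP 5.5 puts the same two sentences side by side for the active metabolite (TAM).

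**Appendix A 1.1.2, individual concentrations and PK parameters.** "If a BLQ value occurs after the last measurable concentration in a profile, the BLQ should be treated as missing data".

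**Appendix A 1.1.2, summaries and mean plots.** "BLQ values will be set to zero". In addition, "Mean concentration at any individual time point will only be calculated if at least half of the subjects have valid values", where valid means quantifiable and not missing; and "GM and GM CV% will not be calculated if there are zero values for concentrations".

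**Appendix A 1.1.4.** AUC and the concentration at each sampling time, post-CPB included, are compared between arms by t-test, or by Mann-Whitney if the assumptions fail. The sample code for this analysis contains "var log_PKParm". The section does not say which A 1.1.2 rule applies to a BLQ concentration in these comparisons.

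**The concern.** In a drug-removal trial a BLQ result after bypass is an observation: the level lies somewhere between 0 and the LLOQ. A sensitivity analysis of the LLOQ assignment should explore that interval. Carry-forward goes outside it, to a value that the assay has shown to be too high.

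In the time-point comparison, a log-scale analysis cannot use a zero and does not use a missing value, so a BLQ subject leaves the test under either Appendix A rule. The device makes post-CPB BLQ more frequent, so the loss depends on treatment and the comparison of those who remain is pulled toward no removal.

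These analyses are outside the confirmatory sequence. They still matter, because protocol section 3 relies on the drug-level measurements to link less bleeding to ticagrelor removal.

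**Working it through.** **1. The plan's own figure.** Key-secondary power, using a 40-point difference, SD 40, two-sided 0.05 and an equal-variance t-test (protocol 11.1 and 11.3, SAP 2). The noncentrality is (40/40) x sqrt(n/2), which is 5.34 at n = 57 and 5.70 at n = 65. Power is 99.96% and 99.99%, so the stated >99.9% reproduces.

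**2. Carry-forward in single subjects.** Removal = (pre - post)/pre x 100.

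| Case | BLQ = LLOQ | Carry-forward | BLQ = LLOQ/2 | BLQ = 0 |
|---|---|---|---|---|
| Pre 100, last on-CPB value 10, post BLQ, LLOQ 5 | 95% | 90% | 97.5% | 100% |
| Pre 2 x LLOQ, every later sample BLQ | 50% | 0% | 75% | 100% |

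The carried value is never below the LLOQ, so carry-forward never gives more removal than the main rule. The truth lies between the first and last numeric columns.

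**3. Carry-forward on average.** Everything here is assumed, because the documents give neither the LLOQ nor clinical baseline levels. Model A: lognormal pre-CPB level, geometric SD 3 to 4, residual log-SD 0.3, 400,000 per arm. Control post-CPB is 0.8 or 1.0 times pre, and the device removes 40% (the plan's figure) or 80% (the bovine-blood figure in protocol 1.2) beyond that. On-CPB samples fall at 30%, 60% and 90% of bypass on a smooth profile. Subjects with a BLQ pre-CPB level are left out of percent change. At a median baseline of 5 to 10 x LLOQ, carry-forward lowers the between-arm difference, relative to the LLOQ rule, by 0.3 to 1.1 points at 40% removal and 2.7 to 6.4 points at 80%.

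Model B: 65 per arm, 400 runs, baseline CV 100%, bypass 60 to 150 min, independent noise in each sample. Mean difference in percent removal:

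| Removal | LLOQ as share of median baseline | BLQ = LLOQ | Carry-forward | BLQ = 0 |
|---|---|---|---|---|
| 40% | 2% | 40.3 | 40.3 | 40.3 |
| 40% | 10% | 39.4 | 38.7 | 41.2 |
| 40% | 20% | 36.6 | 34.9 | 43.8 |
| 80% | 2% | 74.2 | 73.6 | 74.8 |
| 80% | 10% | 69.2 | 64.2 | 77.2 |
| 80% | 20% | 60.9 | 52.0 | 79.4 |

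At 10% and 20% the falls are 0.7 and 1.7 points (40% removal), and 5.0 and 8.9 points (80%). In the same rows, moving from LLOQ to 0 raises the difference by 1.8 and 7.2, and by 8.0 and 18.5 points. The interval that carry-forward ignores is the larger one. The test was significant in every run under each of these rules, and also with BLQ treated as missing.

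**4. Time-point comparison, post-CPB, Model A.** True device/control ratio 0.60:

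| Median baseline | BLQ, device | BLQ, control | Log scale, BLQ dropped | Log scale, LLOQ/2 | Raw scale, BLQ = 0 |
|---|---|---|---|---|---|
| 5 x LLOQ | 17-27% | 8-16% | 0.71-0.75 | 0.60-0.62 | 0.59-0.60 |
| 10 x LLOQ | 6-14% | 2-7% | 0.65-0.70 | 0.60-0.61 | about 0.60 |
| 50 x LLOQ | about 1% or less | below 1% | 0.60-0.62 | 0.60 | 0.60 |

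With 80% removal (true ratio 0.20), dropping BLQ gives 0.41-0.47 at 5 x and 0.32-0.38 at 10 x. At 5 x, LLOQ/2 gives 0.23-0.27 and raw-scale zero gives 0.17-0.19.

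**5. The half-valid rule.** In Model A, device-arm BLQ reaches 50-58% only at 80% removal and 5 x LLOQ. In Model B the rule never suppressed the device mean at 40% removal. At 80% it did so in 3.7% of runs (LLOQ 10% of baseline) and 92.5% of runs (20%).

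**The case against.** The strongest reply is that nothing confirmatory depends on this. The key secondary has one explicit rule, and a conservative one for a BLQ device-arm subject. AUC and TAM are exploratory, and time-point concentrations are not a listed endpoint and are outside the testing sequence in SAP 3.7. All of that stands.

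The log-scale bias also depends on a reading. The variable name in the sample code suggests PK parameters, and AUC is the only one defined in A 1.1.4. No sentence says that concentrations are logged. On the raw scale with BLQ = 0 there is no pull toward no removal. This stands too, so the second defect is conditional. But the code is offered for an analysis that covers AUC and concentrations alike, and the text leaves the BLQ rule open.

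A check that can only lower removal may be defended as a conservative stress test. That fails as a test of the LLOQ assignment, because the substituted value is one the assay has excluded.

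A reader might infer more than the documents support:

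- *The best-cleared device subjects are removed.* BLQ mainly marks a low baseline: in Model B, 67% to 94% of device BLQ samples came from below-median baselines. The zero rule keeps these subjects in the summaries.
- *The summary table goes blank.* Only the mean and geometric mean can be suppressed; A 1.1.3 also lists median, minimum and maximum.
- *Four treatments of one BLQ sample (LLOQ, carry-forward, missing, zero) are a contradiction.* A sensitivity analysis is meant to differ from the main one, and A 1.1.2 separates parameter calculation from summaries by purpose.

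**Conclusion.** The point holds in a limited form and is of minor priority.

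1. The carry-forward check in SAP 5.3.2, and its TAM counterpart in 5.5, does not test the LLOQ assignment. It can only reduce a subject's removal, to 0% where only the pre-CPB sample is measurable. At a median baseline of 5 to 10 x LLOQ the mean difference falls by about 1 point or less at 40% removal and about 3 to 6 points at 80%. With noisier samples (Model B, LLOQ 10% to 20% of baseline) the fall reaches 1.7 and 8.9.
2. The time-point comparison has no stated BLQ rule. If run on the log scale, a true ratio of 0.60 appears as about 0.65 to 0.75 at 5 to 10 x LLOQ. The effect is negligible at 50 x and absent on the raw scale with BLQ = 0.

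Both sizes rest on an assumed LLOQ, baseline spread and residual variation; the documents cannot fix them. The confirmatory key-secondary rule is clear, and its conclusion did not change in any simulated run.

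**What to change.** **SAP 5.3.2 and 5.5.** Replace carry-forward with two re-runs of the percent-change analysis, with post-CPB BLQ set to 0 and to LLOQ/2, and report them beside the LLOQ result as a sensitivity range. They should not be called bounds: one value used in both arms does not bound a between-arm difference when both arms contain BLQ. If strict bounds are wanted, assign 0 in one arm and LLOQ in the other, then reverse.

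**SAP A 1.1.2 and A 1.1.4.** State that BLQ is an observed value in the time-point comparisons. Use the already planned Mann-Whitney test with BLQ as lowest ties, or LLOQ/2 on the log scale when BLQ is infrequent; when it is frequent LLOQ/2 is itself off (0.23-0.27 against a true 0.20 in the 80% case at 5 x LLOQ). Report the number BLQ by arm and time point, and calculate the geometric mean with LLOQ/2 where BLQ is infrequent, so that a single BLQ does not delete it. Say whether the log-scale code applies to AUC only or also to concentrations.

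**Cost.** SAP wording and a few program lines; no new data.
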